4.2.1 Adverse Events

The incidence of all AEs, treatment-related AEs, serious AEs, and deaths are among the secondary endpoints. In addition, the incidence of all high-grade (Grades 3-5), select adverse events (such as pulmonary, gastrointestinal, skin, renal, hepatic, endocrine, and infusion-related or hypersensitivity) of potentially immune-mediated etiology will be analyzed along with the median time to onset and median time to resolution of select adverse events. Resolution of an AE is a subject experiencing complete resolution or improvement to the baseline grade for the AE.

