In order to derive the time-to resolution, overlapping or contiguous select AEs within a specific category (defined in Table A-2) will be collapsed into what will be termed “clustered” select AEs. For example, if a subject (without pre-treatment AE) experienced an AE from 1st to 5th January, another AE (with different PT but within same category) from 6th to 11th January and same AE from 10th to 12th January, these will be collapsed into one clustered select AE from 1st to 12th January. Table A-1 is summarizing key derivation steps for each type of clustered select AEs.

Time-to resolution of select AE (any grade) for a specific category is defined as the longest time from onset to complete resolution or improvement to the grade at baseline among all clustered select AEs in this category experienced by the subject. Events which worsened into grade 5

events (death) or have a resolution date equal to the date of death are considered unresolved. If a clustered select AE is considered as unresolved, the resolution date will be censored to the last known date alive. Improvement to the grade at baseline implies that all different AE events in the clustered select adverse event should at least have improved to the corresponding (i.e. with same preferred term) baseline grade. This measure is defined only for subjects who experienced at least one select AE in the specific category.

The time-to resolution of select AE (grade 3-5) for a specific category is defined similarly with an onset date corresponding to a grade 3-5 select AE.

Time-to resolution of drug-related select AE (any grade or grade 3-5) is defined similarly but restricted to drug-related select AE.

The time-to resolution of select AE (any grade or grade 3-5, drug-related or all) where immune modulating medication was initiated is defined similarly with the additional condition that the subject started an immune modulating medication during the longest select AE resolution period.

Time-to resolution for a specific subcategory is defined similarly but restricted to event of this subcategory.

Table A-1: Derivation of clustered select AE

Type of clustered select AE	Derivation
Any grade	Collapse any on-treatment select AE from the same category
Drug-related of any grade	Collapse any on-treatment drug-related select AE from the same category

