Grade 3-5	Collapse any on-treatment select AE from the same category. Resolution will be based on the onset date of the earliest grade 3-5 records (if no grade 3-5 record, clustered select AE is excluded)
Drug-related of Grade 3-5	Collapse any on-treatment drug-related select AE from the same category Resolution will be based on the onset date of the earliest grade 3-5 record (if no Grade 3-5 record, clustered select AE is excluded)

The algorithm for collapsing select adverse event records is using the following conventions:

For each subject and specified category, the corresponding adverse event records will be collapsed when:

- 1) Multiple adverse event records have the same onset date.
- 2) The onset date of an event record is either the same day or 1 day later than the resolution date of a preceding event record (contiguous events).
- 3) The onset date of an event record is after the onset date and prior to or on the resolution date of a preceding event record (overlapping events).

Table A-2: Select Adverse Events

Category	Subcategory	Preferred Terms	
ENDOCRINE ADVERSE EVENT	ADRENAL DISORDER	ADRENAL INSUFFICIENCY	
		ADRENAL SUPPRESSION	
		ADRENOCORTICAL INSUFFICIENCY ACUTE	
		BLOOD CORTICOTROPHIN DECREASED	
		BLOOD CORTICOTROPHIN INCREASED	
		HYPOTHALAMIC PITUITARY ADRENAL AXIS SUPPRESSION	
		PRIMARY ADRENAL INSUFFICIENCY	
		SECONDARY ADRENOCORTICAL INSUFFICIENCY	
		DIABETES	DIABETES MELLITUS
			DIABETIC KETOACIDOSIS
	FULMINANT TYPE 1 DIABETES MELLITUS		
	LATENT AUTOIMMUNE DIABETES IN ADULTS		
	TYPE 1 DIABETES MELLITUS		
	PITUITARY DISORDER		HYPOPHYSITIS
		HYPOPITUITARISM	
		LYMPHOCYTIC HYPOPHYSITIS	
		THYROID DISORDER	ATROPHIC THYROIDITIS
	AUTOIMMUNE HYPOTHYROIDISM		
	AUTOIMMUNE THYROIDITIS		
	BASEDOW'S DISEASE		
	BLOOD THYROID STIMULATING HORMONE DECREASED		
	BLOOD THYROID STIMULATING HORMONE INCREASED		
	HYPERTHYROIDISM		
	HYPOTHYROIDISM		
	PRIMARY HYPERTHYROIDISM		
	PRIMARY HYPOTHYROIDISM		
	SILENT THYROIDITIS		
	THYROID FUNCTION TEST ABNORMAL		
	THYROID HORMONES DECREASED		
	THYROID HORMONES INCREASED		
	THYROIDITIS		
	THYROIDITIS ACUTE		
THYROXINE DECREASED			
THYROXINE FREE DECREASED			
THYROXINE FREE INCREASED			
THYROXINE INCREASED			
TRI-IODOTHYRONINE UPTAKE INCREASED			
GASTROINTESTINAL ADVERSE EVENT		AUTOIMMUNE COLITIS COLITIS	

Table A-2: Select Adverse Events

Category	Subcategory	Preferred Terms

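### The longest-cluster rule for time to resolution gives no precedence to unresolved clusters, so an earlier, longer, resolved cluster can displace a later fatal or still-open one

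*SAP*

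**What the plan says.** SAP 4.2.1 lists "median time to onset and median time to resolution of select adverse events" among the secondary endpoints. Resolution of high-grade select AEs is also part of the first secondary objective (Protocol 1.3.2, SAP 3.2).

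SAP Appendix 1 derives the measure in three steps.

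1. **Clusters.** Records in one category are merged when they share an onset date, when they are contiguous ("The onset date of an event record is either the same day or 1 day later than the resolution date of a preceding event record"), or when they overlap ("The onset date of an event record is after the onset date and prior to or on the resolution date of a preceding event record").
2. **Status of each cluster.** A cluster resolves only if "all different AE events in the clustered select adverse event should at least have improved to the corresponding" baseline grade. Events that become Grade 5 or "have a resolution date equal to the date of death are considered unresolved". The appendix then states: "If a clustered select AE is considered as unresolved, the resolution date will be censored to the last known date alive".
3. **One value per subject and category.** This value "is defined as the longest time from onset to complete resolution or improvement to the grade at baseline among all clustered select AEs" that the subject had in the category.

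For the Grade 3-5 version, Table A-1 starts the clock at the earliest Grade 3-5 record in the cluster and drops clusters that have none. No sentence ranks an unresolved cluster above a resolved one.

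**The concern.** Steps 2 and 3 can work against each other. Step 2 takes care to call a fatal or open cluster unresolved. Step 3 then picks a cluster by length alone, and the length of a fatal cluster is cut off by death. The faster the death, the shorter the censored time, and the more easily an earlier resolved cluster is selected. The subject then enters the summary as resolved, and the later cluster never reaches it.

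The pattern is foreseeable. Protocol 4.5.5 lets subjects resume treatment after a drug-related AE improves, and lets some start Part II after stopping Part I for an AE. Protocol 4.5.6 provides for events that recur. A resolved cluster followed by a separate one in the same category is thus an expected course.

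The error runs one way, from unresolved to resolved, in a study whose main purpose is to describe toxicity. The version for events treated with immune-modulating medication inherits it, because Appendix 1 ties that condition to the longest resolution period. Medication started only for the displaced cluster would not count.

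**Working it through.** **Reproducing the SAP example.** Records on 1-5, 6-11 and 10-12 January: day 6 is one day after day 5 (contiguous), and day 10 lies between days 6 and 11 (overlapping). The result is one cluster, 1-12 January, as Appendix 1 states.

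**Hypothetical subjects, Grade 3-5 version.** Time = end − onset + 1 (assumed, since Appendix 1 gives no day count). Unresolved clusters end at the last known date alive, taken as the day of death in fatal cases.

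| Pattern | Cluster times | Score as written | Score if unresolved takes precedence |
|---|---|---|---|
| S1: resolved days 30-89; fatal onset 150, death 160 | 60 resolved; 11 censored | **Resolved, 60** | Censored, 11 |
| S2: resolved days 30-89; open from 150, last alive 730 | 60 resolved; 581 censored | Censored, 581 | Same |
| S3: resolved days 30-89; open from 150, last alive 200 | 60 resolved; 51 censored | **Resolved, 60** | Censored, 51 |
| S4: days 30-70; fatal onset 60 (overlap), death 70 | one cluster, 41 censored | Censored, 41 | Same |
| S5: days 30-89; fatal onset 90 (contiguous), death 100 | one cluster, 71 censored | Censored, 71 | Same |
| S6: open from 30 with no resolution date; later event 150-160; last alive 730 | one cluster, 701 censored | Censored, 701 | Same |
| S7: resolved days 30-39; fatal onset 150, death 175 | 10 resolved; 26 censored | Censored, 26 | Same |

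The wrong status needs three things: an earlier resolved cluster, a separate later cluster that is fatal or open, and a censored time for the later one shorter than the earlier one took to resolve.

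**Size, under assumptions.** None of these inputs is in the documents:
- p2, share of subjects with an event who have two separate clusters: 20-40%
- u, share whose last cluster is unresolved: 10-20%
- resolved times exponential with median 4 weeks
- unresolved clusters observed for an exponential time with median m = 2-12 weeks, independent of the resolved times

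P(resolved time exceeds censored time) = 4/(4 + m):
- m = 2: 4/6 = 0.667
- m = 4: 4/8 = 0.50
- m = 12: 4/16 = 0.25
- m = 52: 4/56 = 0.071

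Only the last cluster can be unresolved, because an open record absorbs every later record in its category (S6). A term such as 2u(1 − u), which counts both orders, would therefore be too large.

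- Share of subjects with an unresolved cluster who are scored resolved = p2 × P: 0.2 × 0.25 = 5% to 0.4 × 0.667 = 27%.
- Share of all subjects with an event = p2 × u × P: 0.2 × 0.1 × 0.25 = 0.5% to 0.4 × 0.2 × 0.667 = 5.3%.
- With m = 52, the first share is 0.2 × 0.071 = 1.4% to 0.4 × 0.071 = 2.9%.

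A second assumed set (5-20% with two or more clusters, 5-30% of those ending unresolved, misclassification probability 0.1-0.8) gives 100 × 0.05 × 0.05 × 0.1 = 0.03 to 100 × 0.20 × 0.30 × 0.8 = 4.8 subjects per 100 with an event.

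**Effect on the median.** Simulating the first set at its most extreme corner (p2 = 0.4, u = 0.2, m = 2), the Kaplan-Meier median is 5.75 weeks as written and 5.83 weeks with precedence: (5.83 − 5.75)/5.75 = 1.4%. At p2 = 0.2, u = 0.1, m = 12 it is about 5.2 weeks under both.

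**The case against.** The strongest reply is that this is a narrow case in a descriptive, single-arm secondary summary.

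- For the Grade 3-5 version, both clusters must be on-treatment, in the same category, more than one day apart, and each must contain a Grade 3-5 record. No source supports 20-40% of subjects having two.
- SAP 4.2.3 follows survival for up to 2 years from first dose, and the final analysis waits until all subjects have completed the study. A survivor with an open event will usually be observed for months and scored correctly, as in S2. The short observation times fit rapid deaths, late-starting events and early loss to follow-up.
- The named endpoint is a median, and it hardly moves.
- Protocol 8.3.2 states the resolution endpoint for Grades 3-4, so a fatal example lies at its edge.
- Reporting detail is deferred to Section 7.6.6 of the Core Safety SAP (SAP 7.6.2.2), which was not available. It may already tabulate unresolved events.

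All of this limits the size. None of it supplies a precedence rule or makes S1 and S3 correct. The Grade 3-4 wording does not remove the problem either: SAP Table A-1 defines a Grade 3-5 measure, and S3 involves no death.

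Two stronger readings are tempting. A reader might infer that unresolved high-grade toxicity is under-reported in general. The documents do not support that: five of the seven patterns are scored correctly, the incidence tables use worst grade (SAP 7.6.1.1), and deaths and SAEs are analysed separately (SAP 7.6.3). A reader might also take the longest time to mean the longest among resolved clusters only, in which case S2 and S7 would be scored resolved too. The censoring sentence in Appendix 1 gives each unresolved cluster an end date, so including those clusters is the more natural reading. The SAP should still say so.

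**Conclusion.** The point holds in a limited form. As written, Appendix 1 gives the wrong status to a subject whose earlier, separate, resolved cluster lasted longer than the time from onset of a later fatal or open cluster to last known alive. That conflicts with the appendix's own statement that fatal events are unresolved.

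The mechanism is certain from the text; the size is not. The ranges of 5-27% of subjects with an unresolved cluster and 0.5-5.3% of subjects with an event rest wholly on the assumed inputs, and longer follow-up of open events lowers them. The harm is to resolved and unresolved status and to any counts built on it. It is probably small overall, but it falls on the worst outcomes. It should be corrected because it touches part of the first secondary objective and is cheap to repair.

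**What to change.** Add to the time-to-resolution definition in SAP Appendix 1:

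- If any cluster in the category is unresolved (any Grade 3-5 cluster, for the Grade 3-5 version), the subject is unresolved, the unresolved cluster is used, and its time is censored. The longest resolved cluster is used only when all clusters resolved.
- The same choice of cluster applies to the version restricted to events treated with immune-modulating medication.

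Also report, per category, the number of subjects with any unresolved Grade 3-5 cluster and the number with any fatal one.

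The cost is a sentence or two in the SAP, a small programming change and two counts from data already collected. The reported share resolved becomes slightly less favourable.

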Subject survival status	---see notes---	May be accomplished by visit for the first 100 days and then by visit or phone for up to 2 years from the first dose of combination regimen therapy
Laboratory Tests: Thyroid function tests	X	Includes TSH (reflect to free T3 and free T4 if abnormal results)
Tumor scans	---see notes---	Tumor progression scans are recommended to be completed as required by local standards of care or at the investigator's discretion for up to 2 years.

Table 5.1-4: Follow Up Assessments for Subjects who Discontinue in Part I^a

Procedure	Every 4 Weeks (± 7 days) through 100 Days after last dose of study drug	Notes
Pregnancy Test in WOCBP	X	Completed more frequently if required by local regulations (serum or blood as required by standard of care at the site). Pregnancy testing may be performed at home if an in-office visit is otherwise not required.
Outcomes Assessments		
[REDACTED]	[REDACTED]	[REDACTED]

^a Subjects who discontinue in Part I are recommended to be followed by direct contact (office visit) every 4 weeks (± 7 days) for up to 100 days from the last dose or should coincide with the date of discontinuation (± 7 days) if the date of discontinuation is greater than 4 weeks (± 7 days) after the last dose. Beyond 100 days from the last dose of study therapy, subjects will be followed for ongoing drug-related AEs until resolved, AE symptoms return to baseline, or are deemed irreversible, for up to 2 years from the first dose or until lost to follow-up, withdrawal of study consent, or death, whichever comes first.

Table 5.1-5: Follow Up Assessments for Subjects who Discontinue in Part II

Procedure	FU-X01 (30 days ±7 days)	FU-X02 (70-84 days after FU-X01 ±7 days)	Follow-Up Visits after FU-X02. Every 24 weeks ±2 weeks	Notes
Safety Assessments				
Physical Examination	X	X		Collect weight and ECOG PS. Focused physical examination may be performed if clinically indicated and to assess for potential late emergent study drug related issues.
Vital signs and Oxygen Saturation	X	X		Temperature, BP, HR, RR, O2 saturation by pulse oximetry at rest (also monitor amount of supplemental oxygen if applicable) at any time a subject has any new or worsening respiratory symptoms.
	■	■		

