8.3.2 Secondary Endpoint(s)

The secondary endpoints are:

- Incidence of all high-grade (Grades 3-5), select adverse events
- Median time to onset and median time to resolution (Grades 3-4) of select adverse events
- Resolution of an AE is a subject experiencing complete resolution or improvement to the baseline grade for the AE
- OS is defined as the time from first dosing date to the date of death. A subject who has not died will be censored at last known date alive.
- Safety and tolerability will be measured by the incidence of all AEs, treatment-related AEs, serious AEs, deaths, laboratory abnormalities, and select AEs such as pulmonary, gastrointestinal, skin, renal, hepatic, endocrine, infusion-related, or hypersensitivity.
- The ORR is defined as the number of subjects with a best overall response (BOR) of a complete response (CR) or partial response (PR) divided by the number of all treated subjects. BOR is defined as the best response designation, recorded between the date of first dose and the date of the initial objectively documented tumor progression by the investigator or the date of subsequent therapy, whichever occurs first. For subjects without documented progression or subsequent therapy, all available response designations will contribute to the BOR determination.
- Investigator-assessed PFS is defined as radiological evidence of progression, significant clinical symptomatic progression, or the need to introduce a non-study drug therapy.

[Redacted]

[Redacted]

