7.6.2.2 Select Adverse Events of Potentially Immune-Mediated Etiology

Select adverse events of potentially immune-mediated etiology will be summarized according to their incidence, as well as their time to onset and resolution as described in Section 7.6.6 of the CA209 Core Safety SAP version 5. High grade (Grade 3-5) select adverse events of potentially immune-mediated etiology will also be summarized overall and for each subgroup of interest.

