APPENDIX 1 SELECT ADVERSE EVENTS DEFINITION AND CONVENTIONS

The select Adverse Events (select AEs) consist of a list of preferred terms grouped by specific category (e.g. pulmonary events, gastrointestinal events categories) and by subcategory (e.g. thyroid disorders, diabetes, pituitary, adrenal disorders subcategories). These categories and subcategories are defined by the Sponsor and the list that is most current at the time of analysis will be used. Also, changes may be made to this list with each new version of MedDRA.

For information, the select adverse events defined at the time of finalization of the first version of the document are listed in Table A-2 using MedDRA version 20.1. The final list used for the clinical study report will be included in an Appendix of the CSR.

Time-to onset definition

Time-to onset of select AE (any grade) for a specific category (i.e. pulmonary events, gastrointestinal events, ...) is defined as the time between the day of the first dose of study treatment and the onset date of the earliest select AE (of any grade) in this category.

If the subject did not experience a select AE (of any grade) in the category, time-to onset will be censored at the maximum follow-up time of all subjects in their respective treatment group (i.e. for subjects without an event, follow-up time is defined from first dosing date up to last dosing date +30 days (or 100 days depending on the analysis) if subjects are off treatment and followed for at least 30 days (or 100 days depending on the analysis) , otherwise it is defined up to the last known alive date). The resulting Kaplan-Meier plot will represent the cumulative rate of the select AE (any grade) in the category over time.

Time-to onset of select AE (grade 3-5) for a specific category is defined similarly but restricted to grade 3-5 select AEs.

Time-to onset of drug-related (grade 3-5 or any grade) select AE for a specific category is defined similarly but restricted to drug-related select AEs.

Time-to onset for a specific subcategory is defined similarly but restricted to event of this subcategory.

Time-to resolution definition

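### Time to resolution censors select AEs that are fatal or open at death; if Kaplan-Meier is used and resolutions are fully recorded, the median is too short, by an amount the documents cannot fix

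*SAP*

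**What the plan says.** Median time to resolution is a secondary endpoint in both documents. Protocol 8.3.2 has "Median time to onset and median time to resolution (Grades 3-4) of select adverse events"; SAP 4.2.1 has "median time to onset and median time to resolution of select adverse events", without the grade limit.

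SAP Appendix 1 gives the derivation. Overlapping or contiguous events in a category are merged into clusters, and a subject's time to resolution "is defined as the longest time from onset to complete resolution or improvement to the grade at baseline among all clustered select AEs" in that category. Events that worsen to Grade 5 or "have a resolution date equal to the date of death are considered unresolved". Then: "If a clustered select AE is considered as unresolved, the resolution date will be censored to the last known date alive". The same rule carries over to the Grade 3-5, drug-related and immune-modulating-medication versions.

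For onset, the same appendix takes another route: without an event, "time-to onset will be censored at the maximum follow-up time of all subjects in their respective treatment group". It names Kaplan-Meier for the onset plot.

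No estimator for resolution is named. SAP 7.6.2.2 says that select AEs will be summarised by incidence, "as well as their time to onset and resolution as described in Section 7.6.6 of the CA209 Core Safety SAP version 5".

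**The concern.** Calling these events unresolved is right. The difficulty is the next step. For a subject who has died, the last date known alive is at or just before death, so the event leaves the risk set there. Kaplan-Meier then assumes that this subject would have gone on to resolve at the same rate as those still alive and affected. For an event that killed the subject this cannot be so, and an event open at death from another cause also never resolved. With death censored, one minus Kaplan-Meier is never below the true cumulative incidence of resolution, so its median is never later than the true one.

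The study exists to describe immune-mediated toxicity and its outcome. Resolution is part of the first secondary objective, and time to resolution also goes into the safety reviews (SAP 9.2.1). Survival is followed for about two years in advanced melanoma, so deaths with an event still open are foreseeable.

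A second gap does not depend on the estimator. The rule to take the longest time does not say what happens when a subject has, for example, a resolved cluster of 60 days and a fatal one of 10 days. Read literally, the resolved cluster could represent the subject.

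**Working it through.** **The plan's own figure.** None is given for resolution. The only design figure is the interval for 308 of 615. The exact Clopper-Pearson limits are 46.06% and 54.11%, as stated, but this does not bear on the point.

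**Inputs.** The censoring rule and the two-year horizon come from the SAP. Resolution and death rates are in neither document, so all of them are assumed, with constant hazards: r for resolution, d for death while unresolved.

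**Formulas, with every resolution recorded.**
- Kaplan-Meier with death censored: share resolved by t = 1 − exp(−rt); median = ln2/r.
- Cumulative incidence with death competing: share = r/(r+d) × [1 − exp(−(r+d)t)]; median = −ln[1 − 0.5(r+d)/r]/(r+d).

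**Fast case.** r = ln2/28 per day, and a share f dies unresolved, so r/(r+d) = 1 − f. For f = 0.05, r+d = 0.02476/0.95 = 0.02606, and the median is −ln(1 − 0.5/0.95)/0.02606 = 28.7 days against 28. For f = 0.02 and 0.10 it is 28.3 and 29.5 days.

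**Slower cases.** Worked example with a resolution median of 26 weeks and a death median of 52 weeks: r = 0.02666, d = 0.01333, r+d = 0.03999, r/(r+d) = 0.6667. The median is −ln(1 − 0.75)/0.03999 = 34.7 weeks, against 26 by Kaplan-Meier.

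| Resolution median (= Kaplan-Meier median) | Death median 52 wk | 78 wk | 104 wk | 156 wk |
|---|---|---|---|---|
| 12 wk: true median | 13.4 | 12.9 | 12.7 | 12.4 |
| 26 wk: true median | 34.7 | 30.9 | 29.4 | 28.1 |
| 12 wk: share resolved at week 52 (Kaplan-Meier 95.0%) | 79.2% | 84.0% | 86.5% | 89.2% |
| 26 wk: share resolved at week 52 (Kaplan-Meier 75.0%) | 58.3% | 63.2% | 65.9% | 68.7% |

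The Kaplan-Meier median is short by 0.4 to 1.4 weeks in the 12-week case and by 2.1 to 8.7 weeks in the 26-week case.

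**Holding deaths at maximum follow-up.** In a simulation of 400,000 events (26-week case, follow-up to week 104 from first dose, onset uniform over weeks 0 to 24), treating deaths as the onset rule treats subjects without an event gives medians of 34.5, 30.8, 29.4 and 28.0 weeks. This matches the cumulative incidence to simulation error.

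**Opposing bias.** Take the 26-week case, with the last dose at onset, and suppose that a share q = 0.20 of events has no resolution recorded after 100 days (a = 14.3 weeks). For t > a:
- Kaplan-Meier share = (1−q)(1 − e^(−rt)) + q(1 − e^(−ra)). Since e^(−ra) = 0.683, setting this to 0.5 gives e^(−rt) = 1 − (0.5 − 0.0633)/0.8 = 0.454, so the median is 29.6 weeks at every death rate.
- Cumulative incidence is the same expression with r+d in the exponents and r/(r+d) in front.

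| | Death median 52 wk | 78 wk | 104 wk | 156 wk |
|---|---|---|---|---|
| True median | 34.7 | 30.9 | 29.4 | 28.1 |
| Kaplan-Meier (error) | 29.6 (−5.1) | 29.6 (−1.3) | 29.6 (+0.2) | 29.6 (+1.5) |
| Death competing (error) | 44.1 (+9.4) | 37.2 (+6.3) | 34.8 (+5.4) | 32.8 (+4.7) |

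Here the sign of the Kaplan-Meier error changes, and the competing-event version is further from the truth in all four columns.

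**The case against.** **The estimator is not stated.** This stands. Kaplan-Meier is named for onset, and a censoring rule combined with a median implies it for resolution, but the Core Safety SAP could say otherwise. It could also already report resolved over affected, which would not carry the bias.

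**Only a median is planned.** This stands too. A reader might infer that the trial will publish an inflated percentage resolved at one year. The supplied text plans no such figure, so the week-52 shares above only illustrate the mechanism. Nor is any select-AE category shown to resolve slowly.

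**Direction.** A reader might infer that the bias is clear in the drug-related sets and uncertain only in the all-causality sets, because the footnotes to Protocol Tables 5.1-4 and 5.1-5 say: "Beyond 100 days from the last dose of study therapy, subjects will be followed for ongoing drug-related AEs until resolved". The documents do not support so clean a split. Table 5.1-5 also marks AE and SAE assessment at the 24-weekly visits without limiting it to related events. Protocol 6.1.1 follows every SAE until it resolves or stabilises. Protocol 6.2.1 lets follow-up of any nonserious AE, related or not, end at stabilisation. Late resolutions could be missed in either set.

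**Replacing Kaplan-Meier could make matters worse.** Under the 20% scenario it does, so the competing-event version should accompany the program version and not displace it.

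**The Grades 3-4 label.** If the protocol's label takes fatal clusters out of the endpoint, only events still open at death from another cause are affected. They would still be censored.

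**Nothing is hidden.** A reader might infer that the rule conceals deaths. It does not: fatal events remain in the worst-grade tables (SAP 7.6.1.1) and in the summary of deaths (SAP 7.6.3).

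**Conclusion.** The point holds conditionally. The censoring rule is explicit. If resolution is estimated by Kaplan-Meier and resolutions are fully recorded, the median is too short: negligibly for events that resolve in about four weeks, by about 0.4 to 1.4 weeks at a 12-week resolution median, and by about 2 to 9 weeks at 26 weeks. Any Kaplan-Meier share resolved would be too high. These sizes rest on constant hazards and assumed death medians of 52 to 156 weeks (2 to 10% dying unresolved in the fast case), so the size in this trial is unknown. Where late resolutions go unrecorded, the net direction is uncertain in any set. The measure is descriptive, with no test attached, and the primary incidence is untouched. The change is still worth making, because it concerns a named secondary endpoint of a safety study and needs no new data. Confidence is medium, mainly because the Core Safety SAP was not available.

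**What to change.** In SAP Appendix 1:

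1. For each category and each set, report the number resolved, the number ongoing and alive at last contact, and the number who died unresolved. These counts are informative under any estimator.
2. Keep the program-standard Kaplan-Meier version. Beside it, present time to resolution with subjects who died unresolved held at maximum follow-up, as the onset rule does, or equivalently the cumulative incidence with death as a competing event. Give the median as not reached if 50% is not attained. Note that unrecorded late resolutions would make this second version read too low.
3. State that, when the longest cluster is chosen, a fatal or ongoing cluster takes precedence over a resolved one, so that a resolved cluster cannot stand in for a fatal one.

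The cost is SAP wording and modest extra programming. The drawback is that two versions appear in the report and may differ; the counts in item 1 help the reader to see why.
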